1.3.1. Risks

Risks of furosemide include electrolyte abnormalities (hypokalemia, hypomagnesemia, and hypocalcemia), hypotension, allergic or toxicity-related symptoms (rash, tinnitus, and hearing change), and other symptoms (cramps, dizziness, unusual tiredness/weakness, chest pain, nausea, vomiting, diarrhea, and numbness/tingling). Furosemide-induced ototoxicity can lead to transient or permanent deafness. Ototoxicity primarily occurs with high-dose intravenous therapy (e.g. >240 mg/hr infusions) or at lower doses in patients with kidney function impairment or concurrent use of other ototoxins such as aminoglycosides.

We have chosen our study selection criteria to exclude patients who are at increased risk for furosemide side effects including those with frequent hypotension, cirrhosis, a hearing disorder, or electrolyte abnormalities in the prior 30 days (hypokalemia defined as serum potassium <3.5 mEq/L, hypomagnesemia, defined as serum magnesium <1 mg/dL, and hypocalcemia, defined as serum corrected calcium < 8 mg/dL), and those taking an interacting drug or substance including an aminoglycoside, cisplatin, methotrexate, cyclosporine, adrenocorticotropic hormone (ACTH), lithium, phenytoin, oral/intravenous steroid, or natural licorice.

In the current trial, risks related to furosemide will be reduced through close monitoring of serum electrolytes, patient symptoms (including hearing), BP, and serum and urine furosemide levels. In addition, we will withdraw participants from the study if any of the following occurs during the course of the study: 1) pregnancy; 2) initiation of a non-loop diuretic (spironolactone, eplerenone, ethacrynic acid, thiazides); 3) initiation of an interacting drug (aminoglycoside, methotrexate, cyclosporine, ACTH, lithium, phenytoin, or oral/intravenous steroid); and/or 4) new diagnosis of cirrhosis.

Occurrence of any of the following events will end dose up-titration (defined below): 1) electrolyte abnormalities, 2) side effects attributable to furosemide (e.g. hypotension, allergic or toxicity-related symptoms), and/or 3) patient non-acceptance. If one of these events occur, the participant will return to the prior tolerated furosemide dose. If one of these events occurs at the lowest administered dose, furosemide will be stopped and not re-started.

- Serum potassium <3.2 mEq/L
- Serum magnesium <0.8 mEq/L
- Serum corrected calcium <7.0 mg/dL
- Systolic BP <80 mmHg that a study investigator attributes to study drug-induced hypovolemia

- Patient desires not to continue furosemide
- Patient-reported symptom of severe or very severe
 - Rash
 - Tinnitus
 - Other self-reported symptom plausibly attributed to furosemide
 - Hearing change (also evaluated with the Inner Effectiveness of Auditory Rehabilitation (Inner EAR) instrument*)

*In addition to self-reported hearing change, we will monitor hearing with the Inner EAR instrument. The Inner EAR instrument measures hearing-related function and has good intra-rater reliability, internal consistency, discriminant validity, and responsiveness to change. Instrument scores correlate with pure tone audiometry.³⁸⁻⁴⁰ Scores range from 0 to 100 points. We will refer participants with ≥10-point decline in Inner EAR scores or self-reported hearing loss (any severity) after furosemide initiation and/or dose titration for audiometry testing. Audiometry for all participants is impractical (i.e. expensive, additional clinic visits) and unnecessary given low risk of hearing complications at the proposed doses (maximum 320 mg/ day).³²⁻³⁴

See **Section 7** for additional safety information (e.g. monitoring, adverse events and serious adverse events).

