3.5.3 Preparation and administration of study drug

The study drug, furosemide, will be provided by the UNC Investigational Drug Service (IDS) which will be the Central Pharmacy for the study. Study drug kits will contain 2-week supplies during the dose escalation period (period 1) and 4-week supplies during the follow-up period (period 2). The PI will request the next supply of furosemide from IDS at each 2-week interval. Unless there is a contraindication (e.g. hypokalemia, serious hypotension), the investigator will escalate the furosemide dosing as described in *Sections 1.2 and 3.5.2*. If up-titration is contraindicated, the PI will notify IDS. If down-titration or discontinuation is indicated, the PI will notify IDS. At the end of period 1, participants will be provided with a 4-week supply of furosemide at the indicated dose (week 6). At the week 10 and 14 visits, additional 4-week supplies of furosemide at the indicated dose will be provided.

If the dose escalation schedule is interrupted (e.g., if a participant is hospitalized at the scheduled time of dose escalation and did not take study drug during the hospitalization), dose escalation will be delayed until the participant has had access to the current dose of study drug for a total of two weeks. If, due to considerable delays in dose escalation, a participant has not reached the final dose assignment by their Week 8 visit, the participant will remain at the current dose of study drug for the remainder of the study and the follow-up period (i.e., the 12-week post-escalation period) will be shortened accordingly such that the total duration of study participation is not increased as a result of the delay. For example, if dose escalation is not completed until week 8, the treatment phase will be 10 weeks rather than 12 weeks.

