3.5.4 Participant adherence monitoring

Study drug containers will be returned to study coordinators at the conclusion of each 2-week period during dose escalation (weeks 2, 4 and 6), and at the conclusion of each 4-week period during follow-up (weeks 10, 14 and 18). Pill counts will be performed to assess participant adherence with prescribed study drug.

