3.5.5 Concomitant therapy

Medication use (both oral and intravenous) will be collected at baseline and throughout the course of the study. Nonloop diuretic (e.g. spironolactone, eplerenone, ethacrynic acid, thiazides), aminoglycoside, cisplatin, methotrexate, cyclosporine, ACTH, lithium, phenytoin, and oral/intravenous steroid use are exclusion criteria. If these medications are initiated during follow-up the treating clinician will be contacted by the research team. If the prohibited drug cannot be discontinued, study medication will be withdrawn, and participants will continue to be followed.

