4 STUDY PROCEDURES

4.1 Overview (Tables 2 and 3)

All study visits will occur at the participant's dialysis clinic at routinely scheduled HD treatments.

- There will be one study visit during the baseline period.
- Dose escalation period (period 1): Blood samples will be collected weekly at mid-week treatment visits (i.e. Wednesday or Thursday during weeks -1, 1, 2, 3, 4, 5 and 6) prior to scheduled dose initiation or dose titration. Urine samples will be collected twice during the dose escalation period at mid-week treatment visits (i.e. Wednesday or Thursday during weeks -1 and 5). Study drug visits will be conducted every two weeks at the first weekly treatment (i.e. Monday or Tuesday during weeks 0, 2, 4, and 6). This structure was selected so that blood results will be collected and analyzed the week prior to study drug dose titration. As such, test results will be available prior to potential dose titration. Adherence and symptom assessment visits will be conducted weekly at the first treatment of each week (i.e. Monday or Tuesday during weeks 1, 2, 3, 4, 5 and 6). Hearing

assessments will be conducted every two weeks at the first weekly treatment (i.e. Monday or Tuesday during weeks 2, 4, and 6).

- Follow-up period (period 2): Blood samples will be collected at mid-week treatment visits every 4 weeks (i.e. Wednesday or Thursday during weeks 9, 13 and 17). Study drug visits will be conducted at the first treatment of each of the subsequent weeks (i.e. Monday or Tuesday during weeks 10 and 14). As in the dose escalation period, this structure was selected so that blood results will be available prior to additional study drug administration. Study adherence and symptom assessment visits will be conducted every 2 weeks at the first weekly HD treatment in the scheduled week (i.e. Monday or Tuesday during weeks 8, 10, 12, 14, 16, and 18). Hearing assessments will be conducted every four weeks at the first weekly treatment (i.e. Monday or Tuesday during weeks 10, 14, and 18). Urine sample visits will be conducted at the mid-week treatments of the 12th week and final week of the follow-up period (i.e. Wednesday or Thursday during weeks 12 and 18). All remaining study drug will be returned at the first weekly treatment (i.e. Monday or Tuesday) of week 19. A final pill count (adherence assessment) will be performed upon study drug return (week 19).

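### Section 1.3.1 withdraws from the study anyone who starts a non-loop diuretic or interacting drug, whereas 3.5.5 stops furosemide only if necessary and keeps following them; nothing says which rule prevails

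*Combined protocol and SAP*

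**What the plan says.** Section 1.3.1 lists four events and says "we will withdraw participants from the study if any of the following occurs during the course of the study". The second is the start of a non-loop diuretic. The third is "initiation of an interacting drug (aminoglycoside, methotrexate, cyclosporine, ACTH, lithium, phenytoin, or oral/intravenous steroid". Starting the drug is enough; no condition is attached.

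Section 3.5.5 covers the same classes of drug, plus cisplatin, and sets out two steps. First: "If these medications are initiated during follow-up the treating clinician will be contacted by the research team". Second: "If the prohibited drug cannot be discontinued, study medication will be withdrawn, and participants will continue to be followed".

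Three other sections bear on the question:

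- Section 4.5 says that a participant who stops study medication is not an early withdrawal and stays on the schedule to week 18. A participant who does withdraw gets one early visit with the week 18 assessments.
- Section 6.3.2 asks for all scheduled evaluations to the end of the study whether or not the participant is still on treatment, and rules out imputation. Section 6.3.1 makes all analyses intention-to-treat.
- Section 9.2.1 says an investigator may end participation for a clinical event or other situation that makes continuing contrary to the participant's interest, and refers to 1.3.1 for what those events are.

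**The concern.** Staff who learn that a participant has been given, say, an aminoglycoside or a thiazide find two instructions that cannot both be followed. One ends participation. The other may leave furosemide running and in any case keeps the participant under observation. Section 9.2.1 adds a third, discretionary version.

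The choice affects the data in two ways. First, safety is a primary objective, and the participants who would leave are those just exposed to a drug the protocol treats as hazardous alongside furosemide. Section 1.3.1 itself links ototoxicity to "concurrent use of other ototoxins such as aminoglycosides". Referral for audiometry depends on self-reported hearing loss or a fall in Inner EAR score, both picked up at scheduled study assessments. Second, drop-out is listed under acceptability in 2.1, and the number withdrawing is an acceptability endpoint in 6.2. A withdrawal forced because another clinician prescribed a steroid would be counted there, although it says nothing about whether patients accept furosemide.

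**Working it through.** The plan gives no figure on this point, so there is none to reproduce. The check compares the rules and then counts the assessments that depend on which one is followed.

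**The two rules compared**

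| | 1.3.1 | 3.5.5 |
|---|---|---|
| What triggers action on furosemide | Starting the drug | The drug cannot be discontinued |
| First step | Withdraw from the study | Contact the treating clinician |
| Furosemide | Ends with participation | Stopped only if the other drug must continue |
| Later follow-up | One early-withdrawal visit (4.5) | Continues |
| Cisplatin listed | No | Yes |

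Withdrawal from the study in 1.3.1 cannot be read as merely stopping the tablets, because 4.5 separates the two explicitly.

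**Inputs for the count** (sections 4.1 and 4.4)

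- Hearing: weeks 2, 4, 6, 10, 14, 18. Period 2 has 3 (10, 14, 18).
- Symptoms and acceptance: weeks 1 to 6, then 8, 10, 12, 14, 16, 18. Period 2 has 6.
- 24-hour urine after baseline: weeks 5, 12, 18. Period 2 has 2.
- The early-withdrawal visit in 4.5 supplies 1 of each.

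Net loss = assessments still scheduled − 1.

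**Withdrawn in week 7** (share of period 2)

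- Hearing: 3 − 1 = 2 of 3
- Symptoms and acceptance: 6 − 1 = 5 of 6
- Urine: 2 − 1 = 1 of 2

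**Withdrawn in week 11** (share of period 2)

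- Hearing (14, 18 remain): 2 − 1 = 1 of 3
- Symptoms and acceptance (12, 14, 16, 18 remain): 4 − 1 = 3 of 6
- Urine (12, 18 remain): 2 − 1 = 1 of 2

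**Withdrawn in week 3, after that week's assessments** (share of all post-baseline assessments)

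- Hearing (4, 6, 10, 14, 18 remain): 5 − 1 = 4 of 6
- Symptoms and acceptance (4, 5, 6, 8, 10, 12, 14, 16, 18 remain): 9 − 1 = 8 of 12
- Urine (5, 12, 18 remain): 3 − 1 = 2 of 3

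The three weeks are illustrations, since the documents give no rate or timing for starting these drugs. Blood samples are left out: 4.1 and 4.4 schedule them in different weeks and the 4.5 visit list omits them, which is a separate matter.

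**The case against.** The strongest reply is that the protocol already answers the question. Sections 3.5.5, 4.5 and 6.3.2 all keep a participant who stops furosemide under follow-up, and the outlier is one sentence in a section on risks. This settles which way the correction should go. It does not remove the conflict, because 1.3.1 is working text: 4.3 cites it for the dosing rules and 9.2.1 for ending participation.

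The second reply is that little safety information is lost. Much of this stands. The early-withdrawal visit includes hearing and symptom assessment. Adverse events are tracked for two weeks after the last dose (7.2), unresolved events are followed and later related events are to be reported (7.2.1), and events of interest, including hearing change and tinnitus, are followed to resolution or stabilization (7.3.1). A patient-reported hearing change after an aminoglycoside might also not count towards the symptom endpoint, which leaves out events attributable to other causes; the Inner EAR endpoint has no such clause. And where furosemide would have been stopped anyway, what is lost is off-drug follow-up. What remains is the loss of the scheduled questionnaire checks, which would find a change that the participant does not volunteer.

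The third reply is that 1.3.1 is the more protective rule. That is fair: 3.5.5 as written lets furosemide continue alongside the interacting drug while the clinician is being contacted. The fix has to close that gap.

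A reader might go further and infer that 3.5.5 covers only period 2, leaving period 1 to 1.3.1 alone, because 3.5.4 speaks of containers returned "at the conclusion of each 4-week period during follow-up (weeks 10, 14 and 18". The documents do not support this. Section 3.5.5 opens by covering medication use at baseline and through the whole study. Table 2 and section 4.4 place follow-up sampling from week 1, and 5.1 separates only baseline from follow-up measurements. The natural meaning is any time after baseline, so the two rules conflict in both periods.

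A reader might also infer a loss of power. That does not follow either. A participant withdrawn in week 7 or 11 is due to have given the week 5 urine and gives another at the early visit, and enrolment may reach 40 against a goal of 36.

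**Conclusion.** The conflict is real in the current text and should be corrected. Sections 1.3.1 and 3.5.5 disagree both on whether starting the drug is enough to require action and on whether the participant leaves the study. Applying 1.3.1 would discard scheduled observations that an intention-to-treat plan without imputation means to collect.

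The size is modest. Per participant withdrawn in week 7, a net 2 of 3 hearing and 5 of 6 symptom assessments in period 2 are lost, and one participant is added to the withdrawal count. How many would be affected is unknown; I assume few. The loss arises only if staff follow 1.3.1, and the adverse event provisions in section 7 cover part of it. The point concerns observation of exposed participants and the meaning of the withdrawal count. It does not threaten the main efficacy analysis.

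**What to change.** 1. In 1.3.1, replace the consequence for the second and third triggers with: *study medication is managed as set out in 3.5.5, and the participant stays on scheduled follow-up to week 18.* Leave the pregnancy and cirrhosis rules as they are.
2. In 3.5.5, change *during follow-up* to *during the study*. This is for clarity only.
3. In 3.5.5, require furosemide to be held from the moment the prohibited drug is discovered until that drug has been discontinued, and stopped permanently if it cannot be. The hold must be mandatory; an optional one would not preserve the protection that 1.3.1 gives now.
4. For a hold in period 1, apply the existing interruption rule in 3.5.3, under which "dose escalation will be delayed until the participant has had access to the current dose of study drug for a total of two weeks", including its week 8 limit.
5. Add cisplatin to the third trigger in 1.3.1, to match 3.5.5.
6. Flag outcomes recorded after a prohibited drug was started, so that results can be shown with and without them.

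The cost is a short amendment with IRB review, because a withdrawal rule changes. No visits are added: 3.5.5 already provides for the follow-up, and visits take place at routine dialysis. The drawback is that some retained urine data may be confounded by the added drug, since a thiazide could itself raise urine volume. Item 6 is there for that reason.

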Occurrence of any of the following events will end dose up-titration: 1) electrolyte abnormalities (serum potassium <3.2 mEq/L, serum magnesium <0.8 mEq/L, and/or serum corrected calcium <7 mg/dL); 2) side effects attributable to furosemide (severe or very severe rash, tinnitus, or hearing change); decrease in Inner Effectiveness of Auditory Rehabilitation (Inner EAR) instrument score by more than 10 points; and/or intradialytic systolic BP <80 mmHg that a study investigator attributes to study drug-induced hypovolemia); and/or 3) patient non-acceptance (defined as the

patient reporting unwillingness to take the study drug). If one of these events occur, the participant will return to the prior tolerated oral furosemide dose. If one of these events occurs at the lowest administered dose, oral furosemide will be stopped and not re-started.

During the 12-week follow-up period (period 2), participants who tolerated and accepted furosemide in period 1 will continue their maximally tolerated period 1 furosemide dose during the 12-weeks of follow-up. If a participant has electrolyte abnormalities or other side effects attributable to furosemide in period 2 (i.e. on their period 1 maximally tolerated dose), the dose will be lowered sequentially (i.e. dose de-escalation: $160 \rightarrow 120 \rightarrow 80$ mg twice daily, or, if on alternative dosing due to prior diuretic use, decrease dose by 50%, rounded to the nearest whole tablet strength of existing (i.e. available) furosemide tablet formulations, until tolerated). If side effects persist or if the participant chooses, oral furosemide will be stopped.

Investigational New Drug (IND) exemption status

Oral furosemide is marketed as a prescription drug product and regulated by the U.S. FDA. Furosemide is indicated for edema and hypertension (signs and symptoms of volume overload). Its use in this study will be considered an on-label use. Our study is exempt from IND requirements for the following reasons:

- Oral furosemide is lawfully marketed in the U.S.
- The study is not intended to be reported to the FDA as a well-controlled study in support of a new indication for use and is not intended to be used to support any other significant change in the labeling for the drug.
- The study is not intended to support a significant change in the advertising for the product.

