4.3 Intervention/Treatment procedures (by visits)

During the 6-week dose titration period (period 1), study drug administration visits will occur every 2 weeks on the first day of the participant's weekly, routinely scheduled HD treatments (i.e. Monday or Tuesday during weeks 0, 2, 4, and 6). During the 12-week follow-up period (period 2), study drug administration visits will occur every 4 weeks on the first day of the participant's weekly, routinely scheduled HD treatments (i.e. Monday or Tuesday during weeks 10, 14 and 18).

Dose-titration (period 1)

Week 0:

A. Participants who are not taking oral furosemide at study entry will receive 2-weeks supply of 80 mg oral furosemide twice daily dosing.

- B. Participants who are taking oral furosemide at study entry will receive 2-weeks supply of his/her prescribed oral furosemide dose.
- C. Participants who are taking another loop diuretic (e.g. bumetanide) at study entry will receive 2-weeks supply of an equivalent dose of furosemide (1mg bumetanide = 40 mg furosemide).

Week 2:

- A. Participants who were not taking oral furosemide at study entry and who tolerated the 80 mg twice daily dose (i.e. no hypokalemia, serious hypotension, symptoms, etc.) will receive 2-weeks supply of 120 mg oral furosemide twice daily dosing.
- B. Participants who were taking oral furosemide at study entry and tolerated the first 2 weeks of dosing will receive 2-weeks supply of furosemide dose 50% higher than initial dose, rounded to the nearest whole tablet strength of existing (i.e. available) furosemide tablet formulations (not to exceed 320 mg/day).
- C. Participants who were taking another loop diuretic at study entry and tolerated the first 2 weeks of furosemide dosing will receive 2-weeks supply of furosemide dose 50% higher than their initial dose, rounded to the nearest whole tablet strength of existing (i.e. available) furosemide tablet formulations (not to exceed 320 mg/day).
- D. Participants who did not tolerate the weeks 0 and 1 dose of furosemide will stop furosemide, and it will not be restarted. See below for parameters for determining intolerance.

Week 4:

- A. Participants who were not taking oral furosemide at study entry and who tolerated the 120 mg twice daily dose (i.e. no hypokalemia, serious hypotension, symptoms, etc.) will receive 2-weeks supply of 160 mg oral furosemide twice daily dosing.

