- B. Participants who were taking oral furosemide at study entry and tolerated the last 2 weeks of dosing will receive 2-weeks supply of furosemide dose 50% higher than initial dose, rounded to the nearest whole tablet strength of existing (i.e. available) furosemide tablet formulations (not to exceed 320 mg/day).
- C. Participants who were taking another loop diuretic at study entry and tolerated the last 2 weeks of furosemide dosing will receive 2-weeks supply of furosemide dose 50% higher than initial dose, rounded to the nearest whole tablet strength of existing (i.e. available) furosemide tablet formulations (not to exceed 320 mg/day).
- D. Participants who did not tolerate the weeks 2 and 3 dose of furosemide will return to the prior tolerated oral furosemide dose. See below for parameters for determining intolerance.

Week 6:

- A. Participants who were not taking oral furosemide at study entry and who tolerated the 160 mg twice daily dose (i.e. no hypokalemia, serious hypotension, symptoms, etc.) will receive 4-weeks supply of 160 mg oral furosemide twice daily dosing.
- B. Participants who were taking oral furosemide at study entry and tolerated the last 2-weeks of dosing will receive
 4-weeks supply of that same furosemide dose (not to exceed 320 mg/day).
- C. Participants who were taking another loop diuretic at study entry and tolerated the last 2-weeks of furosemide dosing will receive 4-weeks supply of that same furosemide dose (not to exceed 320 mg/day).
- D. Participants who did not tolerate the weeks 4 and 5 dose of furosemide will return to the prior tolerated oral furosemide dose. See below for parameters for determining intolerance.

As specified in **Section 1.3.1**, occurrence of any of the following events will end dose up-titration: 1) electrolyte abnormalities (serum potassium <3.2 mEq/L, serum magnesium <0.8 mEq/L, and/or serum corrected calcium <7 mg/dL); 2) side effects attributable to furosemide (severe or very severe rash, tinnitus, or hearing change); decrease in Inner Effectiveness of Auditory Rehabilitation (Inner EAR) instrument score by more than 10 points; and/or intradialytic systolic BP <80 mmHg that a study investigator attributes to study drug-induced hypovolemia); and/or 3) patient non-

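### For severe symptoms in period 1, Section 1.3.1 ends up-titration for anything plausibly due to furosemide, but the lists in 1.2, 3.5.2 and 4.3 name only rash, tinnitus and hearing change

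*Combined protocol and SAP*

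**What the plan says.** **Section 1.3.1** sets out the events that end up-titration. Under patient-reported symptoms of severe or very severe grade it has four items: rash, tinnitus, hearing change, and "Other self-reported symptom plausibly attributed to furosemide". The same section counts among the drug's risks "other symptoms (cramps, dizziness, unusual tiredness/weakness, chest pain, nausea, vomiting, diarrhea, and numbness/tingling". After a trigger the participant goes back to the previous tolerated dose; otherwise, "If one of these events occurs at the lowest administered dose, furosemide will be stopped and not re-started".

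**Sections 1.2, 3.5.2 and 4.3** restate the rule. All three give the symptom item as "side effects attributable to furosemide (severe or very severe rash, tinnitus, or hearing change", with no catch-all. They add "decrease in Inner Effectiveness of Auditory Rehabilitation (Inner EAR) instrument score by more than 10 points". Their other triggers are the electrolyte limits, an intradialytic systolic BP below 80 mmHg attributed to the drug, and the participant's unwillingness to continue. Section 4.3 names Section 1.3.1 as its source and then writes "occurrence of any of the following events will end dose up-titration: 1) electrolyte abnormalities".

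**The visit text of 4.3** describes tolerance differently. At week 2, item A covers participants "who tolerated the 80 mg twice daily dose (i.e. no hypokalemia, serious hypotension, symptoms, etc.) will receive 2-weeks supply" of the next dose; weeks 4 and 6 use the same phrase. Items B and C, for prior loop-diuretic users, say only that the dose was tolerated. Item D reads "Participants who did not tolerate the weeks 0 and 1 dose of furosemide will stop furosemide, and it will not be restarted" and sends the reader to the list further down for the parameters. The no-symptoms phrase returns at weeks 10 and 14 for all participants.

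**The concern.** Tolerance of each dose decides the next dose in period 1. It also fixes the maximally tolerated dose, which starts period 2 and which Section 2.1 names in the efficacy hypothesis. If two statements of the rule disagree, dose assignment and participant safety depend on which section staff have in front of them.

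The disagreement falls on the symptoms that Section 6.1 uses to measure tolerability. Under the shorter lists, a participant could have a tolerability event under 6.1 and, on the same dose, be treated as having tolerated it and moved up.

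**Working it through.** The plan gives no figure to reproduce. The check compares the wording and then traces the doses.

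**1. The triggers side by side**

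| Event | 1.3.1 | Lists in 1.2, 3.5.2, 4.3 | 4.3 visit phrase |
|---|---|---|---|
| Severe or very severe rash, tinnitus, hearing change | yes | yes | yes |
| Other severe or very severe symptom plausibly due to furosemide | **yes** | **no** | yes |
| Milder symptom, or one with another cause | no | no | yes, read literally |
| Inner EAR decrease | only as a way of evaluating hearing change | yes, more than 10 points | not named |
| Electrolytes, attributed low systolic BP, unwillingness | yes | yes | in part |

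The second row is the conflict. The third row shows that the visit phrase is a further standard, broader than either list.

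**2. Scope**

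- Section 1.3.1 names 3 allergic or toxicity symptoms and 8 others: 3 + 8 = 11. The shorter lists cover 3, so 8 depend on the catch-all.
- Section 6.1 names 7 tolerability symptoms: cramping, dizziness/pre-syncope, tiredness/weakness, chest pain, nausea, vomiting and diarrhea. The shorter lists cover none of them.

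These counts show how far the gap reaches. They do not show how often it would matter.

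**3. Dose consequence for a diuretic-naive participant**

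Assume one severe symptom attributed to furosemide, outside the three named; a participant willing to continue; no other trigger; and dose changes made at the scheduled drug visits. Daily doses are 2 × 80 = 160, 2 × 120 = 240 and 2 × 160 = 320 mg.

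| Symptom arises on | Week 5 dose, 1.3.1 | Week 5 dose, shorter lists | Period 2 starting dose, 1.3.1 | Period 2 starting dose, shorter lists |
|---|---|---|---|---|
| 80 mg twice daily (weeks 0–1) | 0 (stopped for good) | 320 | 0 | 320 |
| 120 mg twice daily (weeks 2–3) | 160 | 320 | 160 | 320 |
| 160 mg twice daily (weeks 4–5) | 320, or 240 if lowered at once | 320 | 240 | 320 |

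The starting doses for period 2 differ by 320, 160 and 80 mg/day. Week 5 is the only on-treatment urine collection in period 1, so the short-term efficacy result is read at that dose. For prior users the figures depend on their prescribed dose, so no common number applies.

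**4. Whether another rule closes the gap in period 1**

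- Unwillingness does not apply to a participant who wants to go on.
- Section 3.5.3 lets the investigator hold escalation for a contraindication. Its examples are open-ended but include no symptom.
- Section 9.2.1 allows the investigator to end participation, which is not the same as holding or lowering a dose.

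**The case against.** The strongest reply is that there is really one rule. Section 1.3.1 says it defines the events, 4.3 cites it, and 9.2.1 also points to it for the events that may end participation. The other lists are then incomplete copies, and the no-symptoms phrase in 4.3 leans the same way. The study has a single center, and the PI requests each two-week drug supply and reviews events every two weeks. This is the better reading of intent. It does not remove the conflict, because item D sends staff to the incomplete list inside 4.3, and 1.2 and 3.5.2 carry no pointer to 1.3.1 beside their lists.

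A second reply is that the shorter lists may be deliberate. They match the symptom items that 6.1 classes as safety, while cramping, nausea and the rest are classed as tolerability. Deleting the catch-all from 1.3.1 would also make the text consistent. Against this, the 4.3 citation, the 4.3 visit phrase and the period 2 rule all point towards keeping it. One caution stands: the questionnaire in Appendix 13.1 asks about symptoms during dialysis, so the investigator must separate dialysis cramps or fatigue from drug effects.

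A reader might infer that a poorly tolerated dose then runs uncorrected through 12 weeks of period 2. The documents do not support that. Sections 1.2, 3.5.2 and 4.3 lower the dose in period 2 for any furosemide-attributed side effect, with no severity floor, and stop the drug if side effects persist.

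**Conclusion.** The text is wrong as written: 4.3 says it follows 1.3.1 and omits one of its triggers, and 1.2 and 3.5.2 omit the same one. The exposure is mainly escalation within period 1, the dose at the week 5 urine collection, and the dose at which period 2 begins. In the worst traced case that is 320 mg/day against none. The number of participants affected is unknown, because the documents give no rate of severe furosemide-attributed symptoms. The result rests on a willing participant who meets no other trigger.

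Three further inferences go too far:

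- The shorter lists do not stop for rash, tinnitus and hearing change alone; they also have the electrolyte, Inner EAR, blood pressure and unwillingness triggers. The gap concerns patient-reported symptoms only.
- Tolerance in 4.3 is not left undefined, since item D points to a list. The fault is that the list is shorter than its source and narrower than the visit phrase.
- Tolerability data are not lost. The questionnaire records the 6.1 symptoms under either rule, and participants who stop the drug remain in follow-up (Section 4.5).

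**What to change.** Make 1.3.1 the single stopping list.

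1. State the Inner EAR decrease in it as a trigger of its own, and settle the cut-off: the dosing lists require more than 10 points, while 1.3.1 refers for audiometry at 10 or more.
2. In 1.2, 3.5.2 and 4.3, add the catch-all for other severe or very severe self-reported symptoms plausibly attributed to furosemide, or replace each list with a reference to 1.3.1.
3. In 4.3, replace the no-symptoms phrase with a reference to that list for all participants, including prior loop-diuretic users.
4. Use the 1.3.1 attribution standard for titration, and leave the 6.1 attribution wording for the endpoint analysis.

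The change is to protocol wording only. A few participants may settle at a lower dose. Those with the event at the lowest administered dose, including prior users on their own prescribed dose, would stop furosemide, as 1.3.1 already requires. That could slightly reduce entry to period 2; Section 6.4 already provides for extra recruitment if fewer than 30 are eligible.
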